7.2 Assessment of Adverse Event Severity

The determination of AE severity rests on medical judgment of a medically qualified investigator. The site will use the current version of the Common Terminology Criteria for Adverse Events (CTCAE) version 5.0. Event severity will be assessed at event onset and event severity most extreme (CTCAE level). The severity of AEs will be graded using the following definitions:

Grade 1: Mild

Grade 2: Moderate

Grade 3: Severe but not immediately life threatening

Grade 4: Life-threatening consequences

Grade 5: Death related to AE

7.3 Assessment of Causal Relationship

A medically qualified investigator must assess the relationship of any Event to the use of study drug, based on available information, using the following guidelines:

Not related: There is not a reasonable causal relationship between the study drug and the AE.

Unlikely related: No temporal association or cause of the event has been identified, or the drug or biologic cannot be implicated.

Possibly related: There is reasonable evidence to suggest a causal relationship between the drug and AE.

Probably related: There is evidence to suggest a causal relationship between the drug and AE, and the influence of other factors is unlikely.

Definitely related: Clearly related evidence of a causal relationship between drug and AE.

7.4 Expectedness

The expectedness of an SAE shall be determined according to the most current product label. Any SAE that is not identified in nature, severity, or specificity in the current product label is considered unexpected.

7.5 Protocol-Defined ESIs

The following are commonly expected events in JIA and will not be collected as AEs, but will be reported to the study database via the SAE/ESI eCRF.

- Anaphylaxis
- Aplastic anemia
- Bleeding events requiring transfusion or hospital evaluation
- Cardiovascular event (myocardial infarction or stroke)
- Demyelinating disease
- Gastrointestinal perforation
- Hepatic Events
- Hepatitis
- Hypercholesterolemia
- Hypersensitivity reactions
- Infections treated with IV anti-infective(s)
- Inflammatory bowel disease
- Interstitial lung disease
- Leukopenia
- Lipoid pneumonia
- Macrophage activation syndrome
- Malignancy
- Mycobacterium tuberculosis infection
- Myocardial infarction
- Neutropenia
- New autoimmune disease (e.g., systemic lupus erythematosus)
- Optic neuritis
- Other opportunistic infections (Other opportunistic infections (e.g., Legionella, Listeria, systemic infections due to endemic mycoses [Coccidioides, Blastomyces, Histoplasma], Pneumocystis, Aspergillus, Nocardia, Cryptococcus, Toxoplasma, Varicella Reactivation [shingles])
- Pregnancy and pregnancy outcome
- Progressive multifocal leukoencephalopathy (JC virus)
- Psoriasis
- Pulmonary alveolar proteinosis

- Pulmonary hypertension
- Severe injection site reactions
- Stroke
- Thrombocytopenia
- Uveitis
- Worsening of autoimmune diseases (per investigator discretion)

7.6 Serious Adverse Events

A serious adverse event is any untoward medical occurrence that, at any dose:

- Results in death
- Is life-threatening

NOTE: The term ‘life-threatening’ in the definition of ‘serious’ refers to an event in which the participant was at immediate risk of death at the time of the event. It does not refer to an event, which hypothetically might have caused death, if more severe.

- Requires inpatient hospitalization or prolongation of hospitalization unless hospitalization is for:
 - Routine treatment or monitoring of the studied indication, not associated with any deterioration in condition
 - Elective or pre-planned treatment for pre-existing condition that is unrelated to the indication under study and has not worsened since the start of the drug of interest
 - Social reasons and/or respite care in the absence of deterioration in the participant’s general condition
- Results in disability/incapacity.

NOTE: The term disability means a substantial disruption of a person’s ability to conduct normal life functions. This definition is not intended to include experiences of relatively minor medical significance, such as headache, nausea, vomiting, accidental trauma (e.g. sprained ankle) which may interfere or prevent everyday life functions but do not constitute a substantial disruption.

- Is a congenital anomaly or birth defect.
- Medically significant, e.g., defined as an event that jeopardizes the participant or may require medical or surgical intervention to prevent one of the outcomes listed above (e.g. may require treatment on an emergency outpatient basis for an event not fulfilling any of the definitions of a SAE given above and not resulting in hospital admission.

This determination is based on the opinion of either the investigator or sponsor (e.g., if either believes it is serious, it must be considered an SAE).

Regardless of causality, the investigator must report within 24 hours of knowledge of the event, via RAVE EDC system, all SAEs and ESIs occurring between informed consent and Month 12 End of Study Visit or 30 days after the last dose of study drug if early termination from the study. If the eCRF system is temporarily unavailable, the SAE, including investigator-determined causality assessment, should be reported to DCRI Safety Surveillance via a paper back-up SAE form. Upon return of the availability of the EDC system, the most current SAE information must be entered into the eCRF. DCRI Safety Surveillance will notify Bristol Myers Squibb (BMS) of reported SAEs within 2 business days of awareness by DCRI Safety Surveillance.

The investigator must report, via RAVE EDC system, when important follow-up information (final diagnosis, outcome, results of specific investigations, etc.) becomes available after submission of the initial SAE/ESI information. Follow-up information should be submitted according to the same process used for reporting the initial event as described above (i.e., within 24 hours of knowledge, via RAVE EDC system). All SAEs and ESIs will be followed through resolution, stabilization, or end of study.

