3.2 Clinical Trial Inclusion Criteria

To be eligible for this trial, participants must meet all of the following criteria in order to be included in the study:

1. Age \geq 2 years old and \leq 16.5 years old
2. Clinical diagnosis of JIA by a pediatric rheumatologist within the past 6 months
3. Arthritis affecting \leq 4 joints between disease onset and enrollment
4. Enrollment in the CARRA Registry
5. Participants of childbearing potential must agree to remain abstinent or agree to use an effective and medically acceptable form of birth control from the time of written or verbal assent to at least 66 days after taking the last dose of study drug.
6. Weight \geq 50 kg (Canadian Sites only)

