12. JAMAR
13. JADAS
14. SAEs

- 15. ESIs
- 16. ESR/CRP/ CBM/ CMP (Only if obtained as SOC)
- 17. Data entry of SOC labs if available
- 18. Results of urine pregnancy screen -May be repeated at any time during study duration per standard of care by participant's provider.

Month 9/ (+/- 2 weeks; in person or via telehealth)

- 1. Physical Examination
- 2. Joint Exam - active joint count
- 3. Interval history to include interval use of NSAIDs and intra-articular glucocorticoid injections, new co-morbid conditions (including psoriasis), encounters with health care professionals (specifically in response to uveitis, active arthritis, or serious adverse events).
- 4. Concomitant medications
- 5. Ophthalmology exam per Table 3
- 6. Physician Global Assessment
- 7. Parent Global Assessment
- 8. Selected PROMIS® measures – See Table 5
- 9. JADAS
- 10. SAEs
- 11. ESIs
- 12. ESR/CRP/CBC/CMP (Only if obtained as SOC)
- 13. Data entry of SOC labs if available

Month 12 End of Study Visit (+/- 2 weeks; in person only)

- 1. Physical examination
- 2. Joint Exam - active joint count
- 3. Interval history to include interval use of NSAIDs and intra-articular glucocorticoid injections, new co-morbid conditions (including psoriasis), with health care professionals (specifically if related to uveitis, active arthritis, or serious adverse events).
- 4. Concomitant medications
- 5. Ophthalmology exam per Table 3
 - Ophthalmology exam may be up to 4 weeks after the Month 12 visit
 - Record results if performed as part of standard of care.
- 6. Physician Global Assessment
- 7. Parent Global Assessment
- 8. Selected PROMIS® measures – see Table 5
- 9. CHAQ
- 10. JADAS
- 11. SAEs
- 12. ESIs
- 13. ESR/CRP/ CBC/ CMP (Only if obtained as SOC)
- 14. Data entry of SOC labs if available

Interim Visit (in person or via telehealth)

1. Physical examination
2. Joint Exam - Active joint count
3. Interval history to include interval use of NSAIDs and intra-articular glucocorticoid injections, new co-morbid conditions (including psoriasis), encounters with health care professionals (specifically in response to uveitis, active arthritis, or serious adverse events).
4. Concomitant Medications
5. Drug Adherence (If subject is currently taking study drug at time of interim visit)
6. Ophthalmology exam
7. Physician Global Assessment
8. Parent Global Assessment
9. Selected PROMIS® measures – see Table 5

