7.1 Definition

Only Events of Special Interest (ESIs), serious and non-serious, and SAEs will be collected for this study and reported in the RAVE EDC. COVID-19 and related symptoms that meet the criteria of an SAE will be considered unexpected/unanticipated SAEs and reported in the RAVE EDC.

Disease progression will not be reported as an ESI or SAE but will be reflected in the visit joint exams.

Safety will be assessed following initial informed consent, throughout the study and for 30 days post last study dose and it will be assessed by frequency and incidence of ESIs and SAEs. A data safety monitoring board (DSMB) will be convened to review data and safety information from study participants throughout the study.

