7.8 Pregnancy

If, following initiation of abatacept (Orencia), it is subsequently discovered that a study participant is pregnant or may have been pregnant at the time of abatacept (Orencia) exposure, or within 5 half-lives (66 days) after product administration, abatacept (Orencia) will be permanently discontinued in an appropriate manner (e.g., dose tapering if necessary for participant).

During the course of the trial, female study participants will be instructed to contact the site investigator immediately if they become pregnant. The study participant will discontinue study drug. The site investigator must report any pregnancy occurring during the trial on the appropriate Pregnancy Surveillance Form. While pregnancy is not considered an SAE, it must be reported within 24 hours of knowledge of the pregnancy, the same timelines as an SAE. The pregnancy must be followed to determine outcome (including premature termination) and status of mother and infant. The Site PI is responsible for following the participant's pregnancy to final outcome. DCRI Safety Surveillance will notify BMS of any pregnancy within 2 business days of awareness by DCRI Safety Surveillance. Any associated SAEs/ESIs that occur to the mother or fetus/infant will be recorded on the SAE/ESI eCRF, as appropriate.

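### For children who leave early, section 7.6 can end SAE/ESI reporting before they leave the study, contrary to 7.1 and Table 2, and pregnancies found after exit but within the protocol's 66-day window are not clearly reportable

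*Combined protocol and SAP*

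**What the plan says.** **SAE/ESI reporting.** Section 7.6 is the rule sites act on, with a 24-hour clock. Its period is "between informed consent and Month 12 End of Study Visit or 30 days after the last dose of study drug if early termination". Section 7.1 describes safety assessment as running from consent, "throughout the study and for 30 days post last study dose", and makes no exception for early termination. Table 2 marks SAE and ESI review at every visit, including M9, interim visits and the End of Study visit. Footnote 1 to that table also calls for the End of Study visit when a child leaves the study early.

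**Exposure window.** Section 3.2 requires contraception for "at least 66 days after taking the last dose of study drug". Section 7.8 treats a pregnancy as exposed if it falls "within 5 half-lives (66 days) after product administration".

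**Pregnancy reporting.** Section 7.5 lists pregnancy and its outcome as an ESI. Section 7.8 adds a separate duty: "The site investigator must report any pregnancy occurring during the trial on the appropriate Pregnancy Surveillance Form". On timing, "it must be reported within 24 hours of knowledge of the pregnancy, the same timelines as an SAE", and the site follows the pregnancy to its outcome.

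**Pregnancy testing.** Table 2 marks the urine test at enrollment, M3, M6, M9, M12 and interim visits. In section 4.8 the Month 3/Month 6 list has it ("Results of urine pregnancy screen -May be repeated at any time during study duration per standard of care"), but the Month 9, Month 12 and interim lists do not. Section 4.3.2 asks for negative tests throughout the trial.

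**The concern.** Section 7.6 sets two end points that behave differently. For a completer, reporting ends at a study visit. For an early leaver it ends at a date fixed by the last dose, which may come well before the child's last contact with the site. Read literally, 7.6 then lets a site leave out a serious event that it saw while the child was still on study, although 7.1 and Table 2 imply that the event should be collected.

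Section 7.1 says that safety will be summarised by the frequency and incidence of ESIs and SAEs. If sites read the period differently, both the event counts and the follow-up time behind those figures become uncertain for early leavers.

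Pregnancy raises a narrower question. The protocol fixes 66 days as the period in which a pregnancy counts as exposed. For a girl who has left early, however, neither the 30-day ESI limit nor a duty worded in terms of the trial clearly reaches day 66.

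**Working it through.** **Inputs.** 24 weekly doses, with 12 months equal to 48 weeks (synopsis), so M6 is week 24 and M9 is week 36. Visit windows of ±2 weeks (Table 2). The 30-day limit (7.6). The 66-day window (3.2 and 7.8). Assumption: the first dose is on day 0 and no dose is missed or held.

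**The 66-day figure.** Section 7.8 equates it with 5 half-lives, which implies 66 / 5 = 13.2 days per half-life. The documents give no half-life, so the figure cannot be reproduced independently. Sections 3.2 and 7.8 agree on it, and it is used here as the protocol's own.

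**Full course, then early exit**
- Last dose: 23 × 7 = day 161.
- 7.6 limit for an early leaver: 161 + 30 = day 191.
- End of the exposure window: 161 + 66 = day 227.
- M9: 36 × 7 = day 252. An exit there comes 252 − 191 = 61 days after the limit, or 47 to 75 days with the ±14-day window.

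**Drug stopped early, child leaves later.** If the last dose is dose 8, it falls on 7 × 7 = day 49 and the limit on day 79. An exit at week 24 (day 168) comes 168 − 79 = 89 days after the limit.

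**Exit soon after the last dose.** If the last dose is dose 12 (11 × 7 = day 77) and the child leaves at week 12 (day 84), the limit is day 107, which is 23 days after exit. Here 7.6 does not cut off time on study. The exposure window runs to 77 + 66 = day 143, so 143 − 107 = 36 days of it lie beyond the ESI limit and after exit. This is where a pregnancy is not clearly reportable.

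**Completers.** M12 is 48 × 7 = day 336, which is 336 − 161 = 175 days after the last dose (161 to 189 with the visit window). That is well past day 66, so nothing is lost.

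**Pregnancy testing**

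| Visit | Table 2 | Section 4.8 list |
|---|---|---|
| M3, M6 | marked | listed |
| M9 | marked | not listed |
| M12 / End of Study | marked | not listed |
| Interim | marked | not listed |

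Under 4.8 the last listed test is at M6, day 168 (154 to 182 with the window). That is from 7 days before to 21 days after the last dose of a full course. Under Table 2 a test is also due at the End of Study visit, including one held at early exit. Whether a pregnancy is found before or after exit therefore depends partly on which text a site follows.

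**The case against.** The strongest answer is that 7.6 should not be read alone. Section 7.1 covers the whole study with no early-termination exception, Table 2 has SAE/ESI review at every visit, and the End of Study visit is also due at early exit. On that reading the child who leaves at M9 has events reviewed up to the day of leaving. This stands as far as it goes: a reader might infer from 7.6 that such events will go unreported, and the documents do not show that. They show two rules that disagree, and the one that ends sooner is the one that states the sites' reporting duty.

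The second answer is that pregnancy has its own rule in 7.8 with no 30-day limit. That also stands for pregnancies arising and found while the child is in the trial. It does not settle one conceived or discovered after early exit.

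The third is that stopping drug is not leaving the study. Sections 6.4 and 6.4.3 encourage children who stop drug to stay and complete their visits, and they are then covered to Month 12. So it would be wrong to conclude that every child who stops for safety reasons has the shortest follow-up.

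The fourth is that the protocol uses 66 days only for contraception and pregnancy exposure. A reader might infer that all SAE/ESI collection must therefore run to 66 days. Nothing in the documents says so, and that extension is a preference.

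Finally, section 6.4 says that leaving the trial does not by itself end CARRA Registry participation, so later events may be recorded there. The documents do not say that such records reach the trial's safety database.

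**Conclusion.** The point holds as an inconsistency in the reporting rules, with modest consequences.

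- Read literally, 7.6 can close SAE/ESI reporting before an early leaver exits: by 61 days for an M9 exit after a full course, and by 89 days in the dose-8 example. Both figures assume dosing from day 0 without interruption. This conflicts with 7.1 and Table 2, so events in the gap are not clearly required to be reported.
- After early exit, up to 36 days of the protocol's pregnancy exposure window (day 30 to day 66 after the last dose) fall outside the ESI limit, and the wording of 7.8 does not clearly cover them.
- Table 2 and 4.8 disagree on pregnancy testing at M9, M12 and interim visits.

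The number of children affected cannot be derived. It is tempting to take 89 − 80 = 9 from the sample-size section, but that 10% is an allowance for participants not evaluable for the primary endpoint, not a rate of early termination. There is likewise no figure to support a claim that SAE incidence will be understated by a given amount. The primary efficacy analysis does not change.

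**What to change.** 1. Reconcile 7.6 with 7.1 and Table 2, so that SAE/ESI reporting for early leavers runs to the later of study exit and day 30 after the last dose.
2. State in 7.5 and 7.8 that a pregnancy within the protocol's own 66-day window is reportable after early exit, where the family has not refused contact. The sponsor may use the same contact to ask about SAEs and ESIs, but the documents do not oblige it to.
3. Reconcile the 4.8 Month 9, Month 12 and interim lists with Table 2 on pregnancy testing, so that both show the same visits.

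The cost is amendment wording, about one telephone contact per early leaver, and a few extra reports. Where a family has withdrawn consent to contact, the call will not be possible and some of the pregnancy gap will remain.

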7.7 Reporting to Regulatory Authorities

Adverse events which meet the criteria of serious, related to study drug, and unexpected for abatacept (Orencia) per its package insert, may qualify for reporting to regulatory authorities. The site investigator will assess any SAE occurring at their site and evaluate it for relationship to study drug.

Informing US FDA: The site investigator is required to complete and submit a voluntary MedWatch Report to FDA for events confirmed by the sponsor as a suspected, unexpected, serious adverse reaction (SUSAR) at: <https://www.accessdata.fda.gov/scripts/medwatch/>.

Informing Health Canada: Reporting an adverse drug reaction (ADR) (i.e. a SUSAR) to Health Canada is a sponsor obligation. The sponsor or designee will notify Health Canada and all participating investigators of fatal or life-threatening SUSARs no later than 7 calendar days after receipt and of non-fatal or non-life-threatening SUSARs no later than 15 calendar days after receipt via a CIOMS I Form.

Informing the IRB/REB: The site investigator will be responsible for reporting serious adverse events and unanticipated problems involving risks to study participants to their local IRBs/REBs in accordance with local regulations.

7.8 Pregnancy

If, following initiation of abatacept (Orencia), it is subsequently discovered that a study participant is pregnant or may have been pregnant at the time of abatacept (Orencia) exposure, or within 5 half-lives (66 days) after product administration, abatacept (Orencia) will be permanently discontinued in an appropriate manner (e.g., dose tapering if necessary for participant).

During the course of the trial, female study participants will be instructed to contact the site investigator immediately if they become pregnant. The study participant will discontinue study drug. The site investigator must report any pregnancy occurring during the trial on the appropriate Pregnancy Surveillance Form. While pregnancy is not considered an SAE, it must be reported within 24 hours of knowledge of the pregnancy, the same timelines as an SAE. The pregnancy must be followed to determine outcome (including premature termination) and status of mother and infant. The Site PI is responsible for following the participant's pregnancy to final outcome. DCRI Safety Surveillance will notify BMS of any pregnancy within 2 business days of awareness by DCRI Safety Surveillance. Any associated SAEs/ESIs that occur to the mother or fetus/infant will be recorded on the SAE/ESI eCRF, as appropriate.

8 EFFICACY ASSESSMENTS

8.1 Primary Outcome

The primary outcome is the occurrence of any of the following: polyarthritis, active anterior uveitis, or initiation of systemic DMARDs and/or biologics, including systemic glucocorticoids (IV or PO) within 12 months of enrollment.

- (a) Polyarthritis is defined as a cumulative total of ≥ 5 active joints with arthritis since disease onset. The active joint count will be assessed at each study visit from baseline through month 12. Active arthritis is defined as joints with swelling not due to bony enlargement or joints with limitation of motion accompanied by either pain on motion and/or tenderness. For the purposes of counting affected joints, each toe counts as a single joint irrespective of whether it is the proximal interphalangeal joint (PIP), the distal interphalangeal joint (DIP), or both that are affected, consistent with previous clinical trials. Joint counts will be documented using a dedicated case report form (eCRF) at each study visit, tracking both specific joints and number of joints involved.⁶¹
- (b) The presence of active anterior uveitis, defined according to the Standardization of Uveitis Nomenclature for Reporting Clinical Data (SUN criteria) as the presence of one or more cells in each 1mm x 1mm slit beam field (Grade 0.5+, trace cells),⁶² will be assessed at standard of care ophthalmology visits as described by the Heiligenhaus modification of the American Academy of Pediatrics recommendations (see Table 2 in Section 4.3.1). Results will be collected using the existing CARRA Registry uveitis specific eCRF.
- (c) Use of systemic DMARDs and/or biologics, including systemic glucocorticoids (IV or PO) will be captured on the concomitant medication eCRF at each study visit.

